9.3.2 Outcome Assessment

9.3.2.1 Primary Outcome

- Rate of major structural **birth** defects, where a major structural **birth** defect will be defined and classified using the CDC coding manual (CDC, 2007). This method has been previously described by the study investigators and the OTIS Research Group (Chambers et al, 2001) and has been used in previous studies conducted by this group.
 - Time Period: Major structural **birth** defects identified up to 1 year of age by the mother, the health care provider, or identified in the dysmorphological examination will be included in the primary analysis. Defects identified after 12 months to 5 years of age will be described and considered separately in the context of a possible pattern.
 - Confirmation: Independent confirmation of certain defects will be required. For example, a heart murmur thought to represent a ventricular septal defect that is ascertained by the examining dysmorphologist will be included if it is confirmed as a heart defect by cardiac ultrasound. Similarly, a midline cutaneous marker at L2-L3 noted in the dysmorphological examination will be included as occult spinal dysraphism only if confirmed by appropriate imaging studies, and in accordance with the CDC coding manual referenced above.
 - Adjudication: A co-Investigator physician with expertise in teratology, pediatrics, and dysmorphology will act as the primary adjudicator of defects classified using the CDC coding system. Verification of classifications in question are performed in 2 ways: (1) by consultation with a Medical Director for the MACDP, who has an ongoing agreement with the MotherToBaby OTIS studies to consult on classification of cases in question, and (2) through a member of the Scientific Advisory Board who has expertise in this area. At annual meetings of the Board, cases classified with major defects are reviewed and where questions arise regarding appropriate classification, primary records are reviewed by one of the members of the Advisory Board with the relevant qualifications.

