9.4.6 Dysmorphology Evaluation

All live born infants will be examined by one of a team of study-dedicated dysmorphologists, led by a co-investigator from the University of California, San Diego. All members of the team are licensed pediatricians with subspecialty fellowship training in dysmorphology and/or genetics. This team of physicians has been functioning as the specialist examiners for the current MotherToBaby/OTIS Pregnancy Studies and have completed examinations for well over **1400** infants throughout North America as part of this protocol using the same standard procedures as are incorporated in this Registry. The physical examinations evaluate infants for both major and minor structural **birth** defects which provide increased sensitivity for detecting a specific pattern of malformation should one exist. All infants will be examined as soon as is practical, and optimally within the first year of life. The Research Center will group and schedule these follow-up examinations to maximize physician blinding as to exposure status, and to minimize travel time and expense for these types of investigations.

Infant examinations will be conducted using a standard checklist of approximately 130 minor malformations included in a dysmorphology exam form (see [Appendix A, 04.E. Dysmorphology Exam Form](#)). In addition, digital photographs of the infant will be taken to aid in validating any diagnoses.

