9.7.2.5 Analysis of the Primary, Secondary, and Exploratory Endpoint(s)

9.7.2.5.1 Primary Analysis

Comparison of the primary outcome between the Specific Evolocumab-Exposed cohort and Comparison Group I will serve as the primary analysis.

Comparison of the prevalence of major structural **birth** defects between the Specific Evolocumab-Exposed cohort and Comparison Group I will be among all live births and, separately, among all pregnancies excluding those lost to follow-up.

Outcomes that are adjudicated as not associated with drug exposure will be excluded from the primary analysis, but included in a sensitivity analysis ([Section 9.7.2.6](#)).

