9.7.2.6 Sensitivity Analysis

Because early prenatal diagnostic testing is prevalent in the US and increasingly performed prior to the second trimester, it is not feasible to exclude all pregnancies with prior prenatal testing from the analysis. Thus, the Registry will include pregnancies that are enrolled prior to outcome but after a prenatal test has been performed, as long as the test does not indicate a major structural **birth** defect. Because of the possibility that this practice could potentially bias the results, analyses for the primary outcome of major **structural** birth defects will be stratified by use of prenatal testing and on gestational timing of enrollment (prior to prenatal testing).

The intention of the primary endpoint is to analyze pregnancies with evolocumab exposure occurring in the first trimester. In the event that there are exposures in the second and third trimester, sub-analyses will be conducted based on length of exposure and timing of exposure, when feasible.

Outcomes that can be adjudicated as not associated with drug exposure will not be included in the primary analysis. Those outcomes, such as chromosomal and genetic abnormalities, that cannot be adjudicated as not associated with drug exposure will be analyzed in the primary analysis as well as in multiple sensitivity analyses that will be designed to address the specific outcomes observed and are impractical to fully pre-specify. However, they will be in keeping with other ongoing studies, advice received from experts, and current and evolving FDA registry guidance.

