9.7.2.6.4 Other Sensitivity Analysis

Sensitivity analysis excluding chromosomal anomalies is planned.

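### The primary analysis drops defects judged unrelated to the drug, a criterion with no valid counterpart in the unexposed comparison group and no stated equal or blinded application

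*Protocol*

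**What the plan says.** Protocol section 9.7.2.5.1 defines the contrast: "Comparison of the primary outcome between the Specific Evolocumab-Exposed cohort and Comparison Group I will serve as the primary analysis". The same section adds the exclusion, "Outcomes that are adjudicated as not associated with drug exposure will be excluded from the primary analysis, but included in a sensitivity analysis", and points to section 9.7.2.6 for that sensitivity analysis. Section 9.7.2.6 restates the rule: "Outcomes that can be adjudicated as not associated with drug exposure will not be included in the primary analysis". It then describes what stays in: "Those outcomes, such as chromosomal and genetic abnormalities, that cannot be adjudicated as not associated with drug exposure will be analyzed in the primary analysis".

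The sensitivity analyses described in section 9.7.2.6 concern the outcomes that were kept. Section 9.7.2.6.4 adds "Sensitivity analysis excluding chromosomal anomalies is planned". None of these returns the dropped outcomes to the count.

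On adjudication, section 9.3.2.1 says that a co-investigator physician "will act as the primary adjudicator of defects classified using the CDC coding system". That is classification of defects, with no criteria for drug association and no mention of blinding. Blinding appears in section 9.4.6, for the infant examinations only and as an aim: the Research Center will "schedule these follow-up examinations to maximize physician blinding as to exposure status".

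The objective in section 8.1 is an overall combined rate of major structural defects. Section 9.5 powers the study on all such defects taken together.

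**The concern.** An exposed-versus-unexposed RR shows an effect of the drug by comparing total counts, background defects included. Removing cases by a prior judgement about whether the drug was involved puts the conclusion into the numerator. The judgement also cannot be made on the same terms in both cohorts. In Comparison Group I no woman was exposed, so either the question is not asked or the answer is always that the defect is unrelated.

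The study expects about 11 exposed and 6 comparator defects at the effect it is powered for, and about 3 and 6 under no effect. With counts this small, a few individual judgements can decide the primary result of a safety registry.

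**Working it through.** **Inputs.** 71 exposed and 142 Comparison Group I pregnancies, background rate 4%, RR 3.8, two-sided alpha 0.05, Fisher's exact or chi-square test, stated power 84% (section 9.5 and Table 3). The share f of defects that would be dropped is not given in the documents. I take 10%, 20% and one third as an assumed range.

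**The plan's own figure.** The exposed rate is 3.8 × 0.04 = 0.152. The pooled rate is (71 × 0.152 + 142 × 0.04) / 213 = 0.0773. Using the null standard error throughout, SE = √[0.0773 × 0.9227 × (1/71 + 1/142)] = 0.0388, and power = Φ(0.112/0.0388 - 1.96) = 82.2%, close to the stated 84%. Exact enumeration gives 79.7% for chi-square and 76.4% for two-sided Fisher. I use Fisher below. The gap between 84% and 76.4% comes from the method of calculation and has nothing to do with this rule.

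**Application 1: exposed cases only.** RR observed = RR × (1 - f). Fisher power uses rates of 0.152 × (1 - f) and 0.04.

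| f (assumed) | RR observed when true RR = 3.8 | Fisher power |
|---|---|---|
| 0 | 3.80 | 76% |
| 10% | 3.42 | 66% |
| 20% | 3.04 | 55% |
| 1/3 | 2.53 | 38% |

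In whole cases, the expected counts at RR 3.8 are 71 × 0.152 = 10.8 and 142 × 0.04 = 5.7.

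- 11/71 v 6/142: RR 3.67, p = 0.007
- 10 v 6: RR 3.33, p = 0.014
- 9 v 6: RR 3.00, p = 0.043
- 8 v 6: RR 2.67, p = 0.075

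Three exclusions remove significance. Under no effect, 71 × 0.04 = 2.8, so about 3 v 6. Dropping one exposed case gives (2/71)/(6/142) = 0.67 in place of 1.0.

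**Application 2: literal use in both groups.** Every Comparison Group I defect is unassociated with evolocumab, so the comparator count becomes 0 and the RR is undefined. If the three exposed defects expected under no effect were retained, 3/71 v 0/142 gives Fisher p = 0.036, a false signal.

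**Application 3: the same share dropped blind in both groups.** RR = [0.152 × (1 - f)] / [0.04 × (1 - f)] = 3.8, so the RR is unbiased. At f = 20% the rates are 0.1216 and 0.032, and Fisher power is 66%.

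**Which application does the text fix?** None. A symmetric rule would need classes of defect that can be identified without knowing exposure. The one class named is given as an example of what stays in, and no excluded class is listed.

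**The case against.** A reader might infer that the rule can only be applied to exposed pregnancies, and hence that it biases the result towards safety. The documents do not support either statement. Neither section limits the rule to the exposed cohort, and section 9.7.2.6 discusses it by class of outcome, which could be applied to every cohort. The direction then depends on the application: downward, undefined or inflated, or unbiased. This objection stands, and the point is conditional for that reason.

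The sentence about chromosomal and genetic abnormalities can also be read as keeping only those members of the class that cannot be ruled out. That is possible, and nothing in the text says that the remaining exclusions would rest on timing relative to dosing. But neither reading supplies a list that can be applied equally to both cohorts.

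The defects do not vanish from view. Section 9.7.2.5.2 compares the total proportion with Comparison Group II and states no such exclusion there. Section 9.7.2.7 compares the overall rate with the external MACDP surveillance programme. Section 9.8 has the advisory board review accumulating data, and section 11.2 reports every major defect in exposed pregnancies whatever its attribution. These are real safeguards, so the protocol does not conceal the cases. They do not repair the primary estimate.

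Finally, adjudication criteria and blinding are commonly left to a statistical analysis plan, which is not shown. That is fair for the detail. The criterion itself, association with drug exposure, is fixed in the protocol, and it is the criterion that does not suit an exposed-versus-unexposed comparison. The 4% background rate comes from a cited cohort whose own exclusions cannot be seen, so the mismatch with the powering rests on how section 9.5 describes the endpoint.

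**Conclusion.** The point holds in conditional form. Two sections order an exclusion by drug association in the primary comparison. That criterion has no valid counterpart in Comparison Group I, and the text states neither equal application nor blinding for it. It conflicts with the overall combined rate in the objective and with powering on all major structural defects together. The sensitivity analysis that section 9.7.2.5.1 promises for the dropped outcomes is not described in section 9.7.2.6.

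The sizes in the table assume both that only exposed cases are dropped and that f lies between 10% and one third. The protocol states neither assumption. Because the rule governs the primary result and rests on a handful of events, it should be corrected before any comparative analysis.

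**What to change.** Make the primary analysis count every confirmed MACDP-coded major structural defect in the exposed cohort and Comparison Group I regardless of attribution, with classification blind to cohort. Delete the exclusion sentences in sections 9.7.2.5.1 and 9.7.2.6. Confine exclusions to a sensitivity analysis based on a listed set of aetiologies, for example chromosomal or single-gene, applied identically and blind to cohort in every group. Reconcile sections 9.7.2.5.1, 9.7.2.6 and 9.7.2.6.4 so that each says the same about what is counted and what is removed.

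The cost is a wording change to the protocol and the analysis plan, plus masking of cohort at defect classification. No new data are needed. A few defects unrelated to the drug will remain in both arms and pull the RR slightly towards 1.

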9.7.2.5.2 Secondary Analysis

The following will comprise the secondary analyses:

1. Comparison of all secondary outcomes between the Specific Evolocumab-Exposed cohort and Comparison Group I
2. Comparison of the primary and all secondary outcomes between the Specific Evolocumab-Exposed cohort and Comparison Group II

The comparison of the prevalence of the total proportion of major structural **birth** defects between the Specific Evolocumab-Exposed cohort and Comparison Group II will be among all live births and, separately, among all pregnancies excluding those lost to follow-up. The comparison of the prevalence of ≥ 3 minor malformations between the Specific Evolocumab-Exposed cohort and each of the 2 comparison groups will be among children who receive the dysmorphological examination. The comparison of IgG-tetanus antibody status (test negative or indeterminate vs test positive) by group (Exposed, Comparison Group I, Comparison Group II) among those in the biological sample sub-study.

In each cohort we will separately calculate the proportion of all pregnancies ending in live birth, spontaneous abortion, stillbirth, elective termination, and lost to follow-up; crude comparisons will be made between cohorts.

The evaluation for a pattern of minor structural **birth** defects will be conducted using the following steps:

1. A comparison among groups of the proportion of infants with any 3 or more minor structural **birth** defects will be made without regard to pattern
2. Among infants with 3 or more minor **structural birth** defects, the Evolocumab-Exposed group will be examined for evidence of a specific pattern of 3 or more defects in any 2 or more children. If such a pattern is identified, Comparison Groups I and II will be evaluated for any evidence of the same pattern.

In each cohort among all live born infants we will separately calculate the proportion of premature delivery, small for gestational age on weight, length or head circumference, and rates of serious infections, hospitalizations, adverse vaccine reactions, and adverse neurodevelopmental outcomes; crude comparisons will be made between cohorts.

Mean birth weight, length and head circumference for full-term live born infants will be compared between cohorts. Postnatal growth parameters will be compared using the proportion of infants ≤ 10 th centile for sex and age with respect to weight, height, or head circumference.

Among the subset of live born infants who participate in the IgG-tetanus antibody assessment at 6-12 months of age, adequacy of immune response will be compared between groups.

Among mothers who give birth to live born infants, the proportion who breastfeed in the first 6 weeks post-delivery will be compared; also among those who breastfeed, the proportion who breastfed exclusively during the first 2 weeks of life.

At the end of the study or as deemed appropriate in consultation with the Scientific Advisory Board, unadjusted and adjusted comparisons between cohorts will be made. Potential confounders will be examined, and adjusted estimates of exposure effects (along with 95% confidence intervals) will be made using Cox proportional hazards, logistic regression, or linear regression techniques as appropriate. Propensity score methods will be considered for adjusted analyses when more than 1 confounder is identified.

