9.3.2.2.2 Infant Outcomes

- Rate and pattern of minor structural **birth** defects where a minor structural **birth** defect is defined as a structural anomaly (itemized on the study examination form) which has neither cosmetic nor functional significance to the child, and a pattern is defined as the same 3 or more minor structural **birth** defects in 2 or more children (see [Appendix A](#), 04.E. Dymorphology Exam Form). Due to the large variability in the sensitivity and specificity of identification of minor defects, in this study, minor defects are tabulated only in those infants who receive the study-related physical examination. This approach of assessment for clusters is based on prior studies that suggest 3 or more minor malformations is a meaningful cut point ([Leppig et al, 1987](#); [Méhes et al, 1973](#); [Marden et al, 1964](#)).
- Rate of small for gestational age where small for gestational age is defined as birth size (weight, length, or head circumference) \leq 10th centile for sex and gestational age using standard pediatric CDC growth curves for full term or preterm infants ([NCHS, 2000](#); [Olsen et al, 2010](#)).
- Rate of postnatal growth deficiency where postnatal growth deficiency is defined as postnatal size (weight, length, or head circumference) \leq 10th centile for sex and age using standard pediatric growth curves, and adjusted for postnatal age for premature infants if the postnatal measurement is obtained at less than 1 year of age.
- Rate of postnatal serious infections (see [Appendix D](#)) and hospitalizations as assessed throughout the 5-year postnatal follow-up period. Pediatric records will be requested after delivery and then on an annual basis with specific requests for documentation of serious infections and hospitalizations
- Rate of infant reactions to scheduled vaccinations as assessed throughout the 5-year postnatal follow-up period. Pediatric records and a questionnaire regarding vaccine administration according to recommended schedule and any vaccine-related adverse events will be obtained on an annual basis (see [Appendix A](#), 08.12. Vaccine Information Form).
- Infant response to IgG-tetanus antibody as a biological marker to evaluate humoral immune response. To be performed via a heel stick **or venipuncture** and standardized assay test between 6-12 months of age in a subset of infants in each of the study groups, conditional on the consent of the mother.

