9.4.4 Medical Records, Pediatric Evaluations

Upon completion of the outcome interview, each woman will be mailed a packet containing medical records release forms for the delivery hospital, obstetrician (**if the release form has not been received**), pediatrician, internist, cardiologist or other specialty physician if applicable (see [Appendix A](#), Form 09.J. Sample OB Medical Records Release Form). For women whose pregnancies have ended in spontaneous or elective abortion or stillbirth, records release forms will be mailed for the specialty physician's evaluation, if applicable, and if prenatal diagnosis, pathology or autopsy reports are available. Each woman will be asked to sign the forms and to return them along with the **patient** exposure diary. Specific information on maternal cholesterol levels obtained prior to and during pregnancy will be requested for women in the Evolocumab-Exposed group and Comparison Group I.

Upon receipt of the signed medical records release forms, a standard physical evaluation form (see [Appendix A](#), 06.H. Birth Info and Private Pediatrician Form) will be mailed to each pediatrician or other physician responsible for the care of each live born infant. This form includes information on infant size at the time of the latest examination and questions about postnatal complications and congenital anomalies. After delivery, at 1 year of age, and annually thereafter until the child's fifth birthday, a medical records release form for the pediatrician or health care provider caring for the child will be sent to the mother for signature. The signed form along with a standard questionnaire about infant/child growth, congenital malformations, serious infections (see [Appendix D](#) for list of conditions qualifying as serious infection), hospitalizations, and adverse reactions to vaccinations administered is sent to the health care provider (see [Appendix A](#), 07.I. Pediatric One Year Follow-up Form, and 08.I2. Vaccine Information Form).

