9.7.2.4.1 Description of Study Enrollment

Outcome	Analysis Subset
Major Structural Birth Defect Among Live Births	All pregnancies ending in at least 1 live born infant
Major Structural Birth Defects Among All Pregnancies Excluding Lost to Follow-Up	All pregnancies excluding lost to follow-up
Spontaneous Abortion	Pregnancies enrolled prior to 20 weeks' gestation
Stillbirth	Pregnancies enrolled excluding lost to follow-up
Preterm Delivery	Pregnancies enrolled prior to 37 completed weeks' gestation, excluding pregnancies ending in twin or higher order multiple births
Minor Structural Birth Defects	Live born infants who have received the dysmorphology examination
Small for Gestational Age Infants	Live born infants excluding twin or higher order multiple births
Breastfeeding	Pregnancies ending in at least 1 live born infant
Postnatal Growth	Live born infants followed up to 1 year postpartum, excluding twin or higher order multiple births
Serious or Opportunistic Infections	Live born infants followed up to 1 year postpartum
Immune Function	Live born infants who received the tetanus titer testing
Response to vaccines	Live born infants who received at least one vaccine
Neurodevelopment	Live born infants for whom developmental screening questionnaires were completed or face-to-face testing was completed

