a variety of factors which may be related to exposure and to pregnancy outcome, such as maternal cholesterol levels and comorbidities including cardiovascular disease history, obesity, diabetes, and hypertension. The use of a disease-matched comparison group addresses to some extent the issue of confounding by indication.

Misclassification bias due to poor recall is thought to be reduced in prospective study designs such as this. In addition, each subject is interviewed at several predetermined intervals during pregnancy. Misclassification bias regarding outcome is minimized in this study design through the use of a specialized physical examination and a standardized evaluation protocol.

Another strength of the study design is the anticipated minimal lost to follow-up rate. Based on previous experience of the investigators in the MotherToBaby/OTIS Pregnancy Studies, and the frequent subject contact, lost to follow-up is typically < 5% and therefore is not expected to pose a threat to the validity of study results. A subject meeting the criteria for enrollment is considered “lost to follow-up” if follow-up information on the outcome (live birth, fetal loss) is not obtainable, or for a live birth if the birth defect status is designated as “unknown” as of 12 months following the estimated due date. Before a **subject** is designated as lost to follow-up, the subject or reporter receives at least 3 reminder telephone calls (documented in database) followed by written correspondence; alternative contact information that is requested upon enrollment is also utilized. All follow-up attempts are documented. Losses to follow-up are tallied in the Registry Interim Reports. No imputation of missing data is planned.

Finally, the primary strength of the cohort study portion of the Registry is its sensitivity for detection of a pattern of malformation. As the known teratogens are associated with specific patterns of malformation, this study design, by virtue of providing study-related dysmorphological evaluation of prospectively ascertained and exposed infants, has the unique capability of detecting within reasonable limits such a pattern if it exists.

10. Protection of Human Subjects

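### Five-year child outcomes that depend on yearly record releases are compared crudely among all live born infants, with conflicting denominators and no rule for partial record coverage

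*Protocol*

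**What the plan says.** **Collection window.** Protocol section 9.3.2.2.2 defines serious infections and "hospitalizations as assessed throughout the 5-year postnatal follow-up period", and gives vaccine reactions the same 5-year window. The source is the pediatric record: "Pediatric records will be requested after delivery and then on an annual basis with specific requests for documentation of serious infections and hospitalizations".

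**How records are obtained.** Section 9.4.4 sends the mother a form to sign after delivery, at 1 year, and then "annually thereafter until the child's fifth birthday, a medical records release form for the pediatrician or health care provider caring for the child". Each year's data therefore depend on a fresh signature and on the provider replying.

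**Analysis text.** One sentence in section 9.7.2.5.2 opens "In each cohort among all live born infants we will separately calculate the proportion of premature delivery" and goes on to "rates of serious infections, hospitalizations, adverse vaccine reactions, and adverse neurodevelopmental outcomes; crude comparisons will be made between cohorts".

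**Subset table (9.7.2.4.1).** Serious or opportunistic infections: "Live born infants followed up to 1 year postpartum". Vaccine response: "Live born infants who received at least one vaccine". Hospitalizations have no row.

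**Missing data.** Sections 9.2.6, 9.7.2.3 and 9.9 each settle loss to follow-up within 12 months of the due date, on the pregnancy outcome or birth defect status. Section 9.9 adds "No imputation of missing data is planned". Section 10.4 keeps a withdrawn subject's data up to withdrawal in the analysis.

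**The concern.** A crude comparison over a fixed 5-year window is sound only if every child in the denominator is observed for the whole window, or if the denominator is cut to the time observed. Here observation can lapse in any year, and no rule says what happens to a child whose records stop after year 1. If that child stays in the all-live-born denominator, the unrecorded years add to the bottom of the rate and nothing to the top.

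Sections 4 and 7 give the FDA requirement as estimating incidence rates through the first 5 years, including child outcomes tied to humoral immune suppression. Infections, hospitalizations and vaccine reactions bear directly on that. Understated rates weaken the estimate in every cohort, and unequal coverage would also distort the relative risk between cohorts.

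**Working it through.** **1. The plan's own denominators (section 9.5).** With 5% lost to follow-up, 10% spontaneous abortion or stillbirth and 5% elective abortion:
- Exposed: 75 × 0.95 = 71.3 observable pregnancies; × 0.85 = 60.6 live births (or 75 × 0.80 = 60.0). Stated: 71 and 60.
- Each comparison group: 150 × 0.95 = 142.5; × 0.85 = 121.1 (or 150 × 0.80 = 120.0). Stated: 142 and 120.

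The figures reproduce, so the all-live-born denominators are about 60 and 120.

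**2. Stated denominators side by side.**

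| Outcome | Window (9.3.2.2.2) | 9.7.2.5.2 | 9.7.2.4.1 |
|---|---|---|---|
| Serious infections | 5 years | All live born | Followed up to 1 year |
| Hospitalizations | 5 years | All live born | No row |
| Vaccine reactions | 5 years | All live born | At least one vaccine |

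The two sections conflict in two rows, and in the third only the all-live-born denominator is stated. The table does not cure the problem: 1 year of follow-up does not match a 5-year window, and one vaccine received does not mean later doses were covered by records.

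**3. Incomplete observation is built in.** The first subject enrolled in December 2016 (9.2.1) and recruitment runs 10 years (9.2.2), to about December 2026. The study ends in October 2030 (9.2.1). October 2030 minus 5 years is October 2025, so a child born later cannot be observed to age 5 even with perfect retention. A child born in December 2026 would be 3 years 10 months old at the end. Sections 9.2.6 and 9.7.1.3 speak instead of 15 years, which from December 2016 runs to December 2031 and moves the cut-off to December 2026. Women enroll at 7-10 weeks on average (9.5), so the last enrollees deliver after that date too. The shortfall is smaller on that reading but does not vanish.

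**4. Size, as an illustration.** Let c be the fraction of the denominator covered by records. If unrecorded time contributes no events:
- observed rate = true rate × c
- observed RR = true RR × c(exposed) / c(comparison)

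The protocol gives no coverage for these outcomes. The only postnatal counts near to it are in the growth row of Table 3: 46 and 108, against 60 and 120 live births. Then 46/60 = 0.767 and 108/120 = 0.900.

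| Assumed coverage, exposed v comparison | True RR 1.0 reads | True RR 2.0 reads | Rates understated by |
|---|---|---|---|
| 0.767 v 0.900 | 0.767/0.900 = 0.85 | 1.70 | 23% and 10% |
| 0.900 v 0.900 | 1.00 | 2.00 | 10% and 10% |
| 0.900 v 0.767 | 0.900/0.767 = 1.17 | 2.35 | 10% and 23% |

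Understatement appears in every row. The direction of any distortion in the RR depends wholly on which cohort has the poorer coverage.

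**The case against.** **No text scores missing years as event-free.** A reader might take that as the protocol's rule, but it is an inference from the stated denominator. Section 9.7.2.5.2 says proportion for premature delivery and rates for these outcomes, so person-time is not excluded. The statement that nothing will be imputed cuts against the inference, since counting an unobserved year as no event is itself a form of imputation. This limits how firmly the consequence can be put. But 9.3.2.2.1 also uses rate for spontaneous abortion and preterm delivery, which are plain proportions, and no person-time definition appears anywhere.

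**The subset table may govern.** The all-live-born lead-in also covers premature delivery and neurodevelopment, which the table restricts, so it may be loose wording. Some hospitalizations also fall under the infection row, because Appendix D counts any infection leading to hospitalization. That is fair for two of the three outcomes, and there the defect is a contradiction. Other hospitalizations still have no alternative denominator.

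**Other methods are available.** Section 9.7.2.5.2 lists Cox models among the options for adjusted estimates, and an analysis plan not at hand may define person-time. The Cox option is tied to none of these outcomes, and the protocol itself fixes a denominator. A contradiction in stated text is not something merely left for later.

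**Table 3 does not show poorer retention in the exposed cohort.** This stands. The 46 and 108 concern growth only, no reason is given, and section 9.5 applies the same 5% loss to every cohort. The 46 may even be a slip, since 90% of 60 and of 120 would be 54 and 108. At a 10% baseline and RR 2.8, a normal approximation with pooled null variance gives 81.4% power for 54/108 and 77.9% for 46/108, against the stated 82%. Using the null variance throughout gives 80.9% for 46/108, so this check does not settle it.

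**Conclusion.** The point holds as a contradiction plus a badly fixed denominator. Two sections disagree for serious infections and vaccine reactions; hospitalizations have only the all-live-born denominator; and nothing governs records missing in years 2 to 5, although late-born children cannot complete the window. Followed as written, 5-year rates are understated in proportion to the missing coverage, and the RR is distorted if coverage differs between cohorts.

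The 0.85 is an illustration. It assumes that the growth-row fractions apply here and that unrecorded time carries no events. With equal coverage a null RR is unaffected and only the absolute rates suffer.

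A reader might infer that the bias runs toward finding evolocumab safe. The documents do not support this, because they state no coverage by cohort for these outcomes. A reader might also compound the growth-row fractions over five years to reach a larger distortion. No yearly retention and no event hazard for these outcomes appear in the protocol, so such a figure would have no basis in it.

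These are secondary outcomes, but they are central to the stated regulatory purpose, so the text should be changed.

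**What to change.** 1. Reconcile 9.7.2.5.2 with the table in 9.7.2.4.1 so that each outcome has one denominator matching its 5-year window, and add a hospitalization row.
2. For serious infections and hospitalizations, replace the crude all-live-born comparison with events per child-year covered by returned pediatric records (Poisson or negative binomial, log observed time as offset). Time to first event, censored at the last record received, is an alternative.
3. For vaccine reactions, use recorded doses, or child-years with returned vaccine forms.
4. Report record coverage by cohort and by year of follow-up, so that a reader can see whether it differs.

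The cost is about one paragraph of analysis wording, one table row and one coverage table. The records and vaccine forms are already requested every year. Two prices remain: a rate per child-year is less simple to read than a percentage, and both methods assume that a lapse in records is unrelated to the events, which the coverage table helps to judge but cannot prove.
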